5. focused physical examination
6. measurement of waist and hip circumference
7. approximately 50mL of blood during a fasting state will be collected for the following tests:
 - a. liver profile
 - b. complete blood count
 - c. lipid
 - d. insulin
 - e. glucose
 - f. INR
 - g. MDA
 - h. K-18
 - i. TNF-alpha
 - j. IL-10
 - k. alpha and gamma-tocopherols
8. female subjects of child-bearing potential will have pregnancy test and the pregnancy test must be negative to participate in the study
9. a positive urine pregnancy test will be confirmed with a serum pregnancy test

Vitamin E for NASH Treatment in HIV Infected Individuals

10. transient elastography (FibroScan®) will be performed by a trained technician to measure steatosis by Controlled Attenuation Parameter (CAP) and fibrosis by liver stiffness (LSM)
11. MRI will be performed to measure hepatic fat content by PDFF according to the established protocol

Randomization

At the same visit, after the baseline evaluation is completed, subjects will be randomly assigned to either Group A: vitamin E in the form of all natural RRR-alpha tocopherol at 800 IU/d for 6 months (n = 28) or Group B: matching placebo for 6 months (n = 28). We will use a stratified randomization plan based on one factor, diabetes, similar to the recent FLINT trial (142). This will ensure two treatment groups having similar distribution of diabetes. A stratum specific computer-generated randomization list will be prepared by the study statistician to randomly assign study subjects in one of the two treatment groups. A block size of four will be used to ensure balance in number of subjects recruited in the two groups. Participants will be given sufficient drug for daily dosing and will be given detailed instructions about how to take the medicine.

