5.0 Study Procedures

Subjects will take the study medicine daily. They will return for a study visit at weeks 4, 12, 24 and at end of study at week 26. The study visits for weeks 4 and 12 should last about four hours and study visit at week 24 will last about eight hours, and the end of the study visit at week 26 will last about two hours. Total amount of time in the study is about 32 weeks, with six weeks allowed between the screening and randomization visits.

The following study procedures will take place at Week 4:

1. study staff will review medical records with the subject
2. subjects will be asked about any problems they are having
3. subjects will bring back unused medicine to monitor medication compliance
4. subjects will be asked about any medications taken, including supplements
5. subjects will receive sufficient amount of medicine to last until the next study visit approximately eight weeks later
6. AUDIT questionnaire will be administered to detail alcohol use and subjects must score less than 8 to continue participating in the study
7. female subjects of childbearing potential will undergo a urine pregnancy test and the test must be negative to continue participating in the study
8. vital signs will be taken, including height and weight
9. waist and hip circumference will be measured
10. subjects will undergo a focused physical examination
11. transient elastography (FibroScan®) will be performed by a trained technician to measure steatosis by Controlled Attenuation Parameter (CAP) and fibrosis by liver stiffness (LSM)
12. historical laboratory values will be captured from the medical records, including
 - a. HIV viral load
 - b. CD4 count

The following study procedures will take place at Week 12:

1. study staff will review medical records with the subject
2. subjects will be asked about any problems they are having
3. subjects will bring back unused medicine to monitor medication compliance

Vitamin E for NASH Treatment in HIV Infected Individuals

4. subjects will be asked about any medications taken, including supplements.
5. subjects will receive sufficient amount of medicine to last until the next study visit approximately twelve weeks later.
6. AUDIT questionnaire will be administered and subjects must score less than 8 to continue participating in the study
7. female subjects of childbearing potential will undergo a urine pregnancy test and the test must be negative to continue participating in the study

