Interval medical history and anthropometric measurements		X	X	X	X	
AUDIT questionnaire	X	X	X	X	X	
Assessment of compliance			X	X	X	
Review of concomitant medicines	X	X	X	X	X	
Review of adverse events			X	X	X	X
Physical examination	X	X	X	X	X	X
Dispensing study medicines		X	X	X		
Blood sample collection		X		X	X	
Urine pregnancy test	X	X	X	X	X	
Liver stiffness and CAP by TE		X	X	X	X	
MR-PDFF		X				X
Biobanking		X	X	X	X	

6.0 Reporting of Adverse Events or Unanticipated Problems involving Risks to Participants or Others

Data will be captured systematically with regards to new medications, over-the-counter medications and supplements, alcohol intake (if any), dietary intake, and changes in weight or physical activity. Patients will be instructed not to take any new medication unless reviewed with and approved by the study PI (wherever possible). During the trial, subjects will be instructed to avoid medications or supplements that may affect the primary outcome (as detailed in the inclusion and exclusion criteria).

Vitamin E for NASH Treatment in HIV Infected Individuals

Risks of blood draw include pain and bruising at the site. Blood will be drawn by experienced personnel.

Risks of completing the questionnaires include embarrassment or being uncomfortable with the questions asked. Subjects can refuse to answer any questions to which they do not wish to respond.

Risks of transient elastography include being uncomfortable lying supine pain, soreness at the site and a small chance of allergic reaction to the ultrasound gel. These study procedures will be performed by experienced personnel.

Risks of MRI include being uncomfortable lying still for a period of time and experiencing claustrophobia (feeling closed in or trapped).

Risks of taking Vitamin E include allergic skin reactions (inflammation or itching), blurred vision, changes in cholesterol levels, changes in insulin resistance, diarrhea, dizziness, fatigue, flu-like symptoms, headache, heart conditions, increased risk of death, increased risk of fainting or falls, increased risk of heart failure, increased risk of high blood pressure in pregnancy, increased risk of stroke, increased risk of tuberculosis, kidney dysfunction, nausea, severe response to infection (in preterm babies), sexual dysfunction, stomach pain, vision loss, and weakness.

There is a risk of loss of confidentiality.

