All endpoints are measured as the change from baseline to 24 weeks. The primary outcome measure is the change in hepatic fat content as measured by central reading of MR-PDFF performed at baseline and end of study. Secondary endpoints will be changes in inflammatory markers (liver enzymes, TNF-alpha, IL-10 levels), serum K-18, Liver stiffness and CAP measurement by TE, and MDA level as a marker of oxidative stress.

The primary outcome is the improvement in liver fat as assessed by MR-PDFF at end of treatment compared to baseline. To our knowledge, there are no data on studying the effect of vitamin E on MR-PDFF in NASH patients with HIV. Using an alpha of 5% and a two-sample independent t-test and equal variance assumption, a sample size of 25 per group will have 91% power to detect an effect size of 0.97 and will have 80% power to detect an effect size as small as 0.81. To ensure this number is achieved, 28 subjects per group will be recruited, allowing for 10% drop-out during the trial. The primary purpose of this pilot study is to generate preliminary data to estimate the mean and variability of improvement in liver fat with vitamin E in HIV infected patients with NASH.

Primary outcomes analysis: The primary analysis will be based on an analysis of covariance (ANCOVA) to compare the improvement in liver fat due to vitamin E relative to placebo. The model will include one dummy variable for treatment group indicator as well as baseline demographic characteristics and baseline liver fat. The 95% confidence intervals for the difference between the two treatment groups will be reported.

Secondary outcomes analysis: Secondary efficacy end points are continuous and as such the ANCOVA model will be used as described for analyzing the primary outcome except that the model will include the baseline value of the response variable.

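### CAP and liver stiffness are read at weeks 4, 12 and 24, but the planned ANCOVA uses only baseline and week 24, so the interim readings go unused and patients without a week-24 reading fall out

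*SAP*

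**What the plan says.** The SAP (Statistical Considerations) and Protocol section 8.0 carry the same text. It lists among the secondary endpoints "Liver stiffness and CAP measurement by TE, and MDA level as a marker of oxidative stress", and sets one time frame for everything: "All endpoints are measured as the change from baseline to 24 weeks". For the secondary endpoints, "the ANCOVA model will be used as described for analyzing the primary outcome except that the model will include the baseline value of the response".

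Elastography is scheduled more often than that analysis needs. Protocol section 4.0 places it at the randomization visit. Section 5.0 places it at weeks 4, 12 and 24. The schedule table row "Liver stiffness and CAP by TE" has the same four marks.

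Section 5.0 also lets patients leave at the interim visits. At weeks 4 and 12, "subjects must score less than 8 to continue participating in the study", where the score is the AUDIT score, and a negative pregnancy test is required in women of childbearing potential.

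Neither document names an imputation method, an analysis population or a missing-data assumption. Drop-out is dealt with only by recruiting 28 per group so that 25 remain.

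**The concern.** Up to 112 on-treatment elastography examinations (56 patients at two visits) have no stated analysis. These are the only efficacy endpoints that study procedures measure between baseline and week 24, since MR-PDFF and the secondary blood markers are scheduled only at baseline and end of treatment.

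A patient with no week-24 reading has no change score, so the ANCOVA as written becomes an analysis of completers. That is safe if loss is unrelated to the patient's course after baseline. If patients leave because of how weeks 4 or 12 went, or if an alcohol-related removal goes with a worse liver course, the week-24 comparison can be distorted. A likelihood-based repeated-measures model conditions on the interim readings that exist, so it needs only that loss be explained by observed values. At stake are a little precision and a little bias in two secondary endpoints.

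**Working it through.** **Inputs from the documents.** 28 recruited and 25 retained per group; 10% drop-out; elastography at four visits; "Using an alpha of 5% and a two-sample independent t-test and equal variance assumption". Two-sided testing is assumed, as the sidedness is not stated.

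**Inputs assumed.** The documents give no correlation between visits for CAP or stiffness and no drop-out pattern. Two families are used: exchangeable correlation of 0.5 to 0.8, and first-order autoregressive correlation of 0.7 to 0.9 between adjacent visits.

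**1. The plan's own figures.** Exact noncentral-t power with 25 per group is 91.9% at an effect size of 0.97 (stated 91%) and 80.1% at 0.81 (stated 80%). 25/(1 − 0.10) = 27.8, so 28 per group. These reproduce. They concern MR-PDFF; no power is stated for CAP or stiffness.

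**2. Patients at issue.** 56 × 0.10 = 5.6, so about 6, or 28 − 25 = 3 per arm. This is a ceiling, since a leaver contributes only if an interim reading was taken.

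**3. Effective sample size at week 24.** With loss unrelated to outcome,

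n_eff = 1 / [(1 − R²)/25 + R²/28],

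where R² is the share of week-24 variance left after baseline that the interim readings explain.

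Example, exchangeable 0.7 with both interim readings. The residual variance given baseline is 1 − 0.49 = 0.51. Given all three earlier readings it is 1 − 3(0.49)/(1 + 2 × 0.7) = 0.3875. So R² = 1 − 0.3875/0.51 = 0.240, and n_eff = 1/(0.760/25 + 0.240/28) = 25.66.

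| Assumed correlation | n_eff, leavers have week 4 only | n_eff, leavers have weeks 4 and 12 |
|---|---|---|
| Exchangeable 0.5 | 25.30 | 25.45 |
| Exchangeable 0.7 | 25.46 | 25.66 |
| Exchangeable 0.8 | 25.54 | 25.75 |
| Autoregressive 0.7 | 25.38 | 26.18 |
| Autoregressive 0.8 | 25.55 | 26.45 |
| Autoregressive 0.9 | 25.73 | 26.70 |

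The variance falls by 1 − 25/25.30 = 1.2% at the low end and 1 − 25/26.70 = 6.4% at the high end. At an illustrative effect size of 0.81, power moves from 80.1% to between 80.6% and 82.7%. With no loss at all (28 per arm) it would be 84.5%.

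**4. Simulation.** 28 per arm, 6,000 runs per setting, exchangeable correlation 0.5, 0.7 or 0.8, true effect −0.81 SD, all loss after week 12. The ratio of the ANCOVA variance to the repeated-measures variance, with loss at random, was 1.015-1.020 at 10% loss and 1.018-1.054 at 20%.

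| Loss depending on the week-12 value | Completer ANCOVA | Repeated measures |
|---|---|---|
| 10% in each arm | −0.793 to −0.805 | −0.802 to −0.810 |
| Nominal 15% in one arm, 5% in the other | −0.777 to −0.792 | −0.805 to −0.812 |

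In the unequal case ANCOVA falls short by 0.018/0.81 = 2.2% to 0.033/0.81 = 4.1%; the repeated-measures estimate stays within 0.005 of the truth. Simulation error on each mean is at most about 0.249/√6000 = 0.003.

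**The case against.** A prespecified single-time-point ANCOVA is a legitimate analysis, and interim measurement does not oblige anyone to fit a longitudinal model. The effect is small, confined to two secondary endpoints of a pilot trial. All of that stands, and it is why this is only an optional improvement.

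Several stronger readings are tempting, and the documents do not support them:

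- **That every leaver would be recovered.** Only those with a week-4 or week-12 reading would be.
- **That patients removed at an interim visit necessarily have a post-baseline reading.** In the week-4 list AUDIT is item 6, the pregnancy test item 7 and elastography item 11; week 12 has the same order. The protocol does not say whether the lists are chronological or whether a removed patient still has the scan. A week-4 removal may have no post-baseline reading, and a week-12 removal only the week-4 one.
- **That the choice of six months rests on when CAP or stiffness responds.** Protocol section 2.0 rests it on ALT and histology in cited studies.
- **That the plan states a completers-only rule.** It does not; the exclusion follows from the plan's silence. A patient who stops treatment but attends week 24 would still count.

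The simulation also places all loss after week 12 with that reading in hand, which favours repeated measures; the AUDIT and pregnancy rules act at or before week 12. And AUDIT removal is driven by alcohol, which would not be in the model, so loss explained by observed CAP or stiffness is not established for those patients. Multiple imputation using the interim readings would be an acceptable alternative.

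**Conclusion.** The point holds as a minor one. The plan collects interim CAP and stiffness readings, states no use for them, and as written omits patients who lack a week-24 reading even where an interim reading exists. A repeated-measures model is better at almost no cost, but the gain is small: less than 2 effective patients per arm and under 3 points of power at 10% drop-out. It largely removes a bias of up to about 4% in the settings simulated, if loss depends on interim values that were observed. These sizes rest on assumed correlations and loss patterns, and the lower end applies if leavers have only a week-4 reading. At most about 6 of 56 patients are involved. A reader might infer that the trial's main result is affected; it is not, because MR-PDFF has no interim scan and the sample size rests on it alone.

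**What to change.** For CAP and liver stiffness only, replace the week-24 ANCOVA with a mixed model for repeated measures on weeks 4, 12 and 24. Include treatment, visit, treatment by visit, baseline value by visit, and the baseline demographic covariates already planned for the ANCOVA, with an unstructured covariance. Report the week-24 treatment difference and its 95% confidence interval as the secondary result, and state the missing-data assumption. Keep ANCOVA for endpoints measured only at baseline and week 24. Adding the diabetes stratification factor would be a separate, optional change.

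The cost is SAP wording; no visit or measurement is added. The one downside is that the model may fail to converge with 56 patients, so a fallback covariance structure should be named in advance.

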3.0 Inclusion/Exclusion Criteria

Inclusion criteria:

1. males and females ≥21 years with biopsy-proven NASH within 6 months prior to enrollment
2. histological diagnosis of NASH will be confirmed by an experienced liver pathologist before study entry
3. HIV infection
4. stable dose of anti-diabetic agents and ART in the 3 months preceding enrollment and expected by the physician treating diabetes and HIV to remain on stable medications during the study
5. stable dose of tesamorelin in the 6 months preceding enrollment
6. willingness to participate in the study
7. ability to understand and give informed consent for participation
8. willing to stop use of Vitamin E and/or multivitamins containing Vitamin E at time of enrollment and for the duration of participation in the study

Exclusion Criteria:

1. Presence of other chronic liver diseases (hepatitis B or C, autoimmune hepatitis, cholestatic liver disease, Wilson disease, hemochromatosis, etc.)
2. average alcohol consumption >3 drinks/day for men or >2 drinks/day for women in the 6 months prior to enrollment.

Vitamin E for NASH Treatment in HIV Infected Individuals

3. Alcohol Use Disorder Identification Test (AUDIT) score 8 or more
4. ongoing use of medications known to cause hepatic steatosis (e.g., corticosteroids, amiodarone, methotrexate, tetracycline, tamoxifen, estrogens at doses greater than those used for birth control, anabolic steroids, or valproic acid)
5. prior bariatric surgery
6. severe co-morbidities (e.g., advanced cardiac, renal, pulmonary, or psychiatric illness, as defined as at least one suicide attempt in the past 12 months)
7. allergy to vitamin E
8. use of drugs with potential effect on NASH such as ursodeoxycholic acid, S-adenosylmethionine (SAM-e), betaine, pentoxifylline, or milk thistle in the three months prior to enrollment.
9. changing doses of statins (simvastatin, pravastatin, atorvastatin, fluvastatin, lovastatin, rosuvastatin) or fibrates (clofibrate, fenofibrate) in the three months prior enrollment.
10. illicit substance abuse within the past twelve months, except for marijuana
11. breast feeding, pregnancy, inability or unwillingness to practice contraception for the duration of the study
12. contraindications for the MRI procedure (e.g., prostheses, severe claustrophobia).
13. poorly controlled diabetes with A1C >9 within in the last six months
14. use of total parenteral nutrition in the 6 months preceding liver biopsy or enrollment

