4.0 Enrollment/Randomization

Participants found to have NASH will be reviewed for their eligibility to participate in this protocol. Eligible subjects will be contacted about this study and interested individuals will enter the screening phase of the protocol.

Screening period: Eligible subjects will be screened within six weeks prior to randomization. The following procedures will take place at the screening visit:

1. Complete explanation of the study, including all study visits and procedures and administration of the informed consent statement and HIPAA Authorization form.
2. An AUDIT questionnaire to determine alcohol consumption will be administered. Eligible subjects will be required to obtain a score of less than 8 on the questionnaire.
3. Current social and medical history will be thoroughly reviewed.
4. Inclusion and exclusion criteria will be verified during this visit.
5. Female subjects of child-bearing potential will have a urine pregnancy test and the pregnancy test must be negative to participate in the study
6. Information to be collected includes:
 - a. age
 - b. sex
 - c. race
 - d. ethnicity
 - e. past medical and medicinal history
 - f. BMI

Vitamin E for NASH Treatment in HIV Infected Individuals

- g. waist and hip circumference measurements
- h. vital signs, including blood pressure, respiratory rate, heart rate, temperature
- i. historical laboratory values from medical records, including:
 - i. serum electrolytes
 - ii. liver profile
 - iii. renal parameters
 - iv. insulin
 - v. glucose
 - vi. A1C level
 - vii. lipid profile
 - viii. HIV viral load
 - ix. CD4 count

Randomization-baseline evaluation visit

1. Subjects will return no more than six weeks after the completion of the screening visit for a baseline evaluation and randomization into the study. All eligible subjects who have provided informed consent and who have met all the inclusion criteria and none of the exclusion criteria will have multiple evaluations performed prior to randomization. This baseline evaluation will be conducted in a single study visit. Subjects will be asked to fast overnight and will undergo the following activities: review of medical history
2. detailed review of medications history
3. administration of the AUDIT questionnaire to capture alcohol use with a score less than 8 in order to participate in the study
4. collection of vital signs
 - a. height
 - b. weight
 - c. blood pressure
 - d. heart rate
 - e. respiratory rate
 - f. temperature

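### Randomisation is stratified by diabetes, but the primary and secondary ANCOVA models do not name the stratum as a covariate

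*SAP*

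**What the plan says.** **Randomisation (Protocol 4.0, Randomization).** "We will use a stratified randomization plan based on one factor, diabetes". The stated aim is balance: "This will ensure two treatment groups having similar distribution of diabetes". Each stratum has its own list, and "A block size of four will be used to ensure balance in number of subjects recruited in the two groups".

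**Primary analysis (SAP, Primary outcomes analysis; same text in Protocol 8.0).** "The model will include one dummy variable for treatment group indicator as well as baseline demographic characteristics and baseline liver fat". The 95% CI for the treatment difference is to be reported.

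**Secondary analysis (SAP, Secondary outcomes analysis).** For these endpoints "the ANCOVA model will be used as described for analyzing the primary outcome", with each endpoint's own baseline value in the model.

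Neither document names diabetes or the randomisation stratum as a model term, and neither lists the demographic covariates.

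**The concern.** Blocking within diabetes strata keeps the arms nearly balanced on diabetes. If diabetes is prognostic, that balance lowers the true sampling variance of the treatment difference. A model without diabetes cannot see this: it counts the between-stratum variation as residual error, so its standard error exceeds the true sampling SD. The nominal 5% test then rejects less than 5% of the time under the null, the CI over-covers, and the precision that stratification can provide is lost. Because the secondary models follow the primary one, this applies to every efficacy endpoint on which diabetes is prognostic.

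The pilot's declared main purpose is to estimate the mean and variability of the improvement in liver fat, and Protocol 7.0 sees it as possible justification for larger trials. The interval and residual variance it reports may therefore be used in later planning.

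**Working it through.** **1. The plan's own figures.** Inputs: 25 per group, alpha 5% (taken as two-sided), two-sample t-test, effect sizes 0.97 and 0.81. With df = 2 × 25 − 2 = 48 and noncentrality d × √(25/2):
- d = 0.97: 0.97 × 3.536 = 3.43, power 91.9% (stated 91%).
- d = 0.81: 0.81 × 3.536 = 2.86, power 80.1% (stated 80%).
- Dropout: 25 / (1 − 0.10) = 27.8, rounded up to 28 per group.

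These agree closely enough. They rest on an unadjusted t-test, so the choice of covariates does not alter them.

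**2. Size expected from theory.** Let R² be the share of outcome variance left after baseline that diabetes explains. With near-perfect balance, the model omitting diabetes has SE² of about 4σ²/n, and the model including it about 4σ²(1 − R²)/n. The CI width ratio, omitted to included, is then about 1/√(1 − R²):
- R² = 0.05: 1/√0.95 = 1.026
- R² = 0.10: 1/√0.90 = 1.054
- R² = 0.20: 1/√0.80 = 1.118

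**3. Simulation at the trial's size.**
- From the documents: 56 randomised 1:1 in blocks of four within diabetes strata; about 10% dropout, taken as 6 lost at random, so 50 analysed; ANCOVA; effect size 0.81 for power.
- Assumed: 40% diabetic; R² of 0, 0.05, 0.10 or 0.20; outcome SD 1 after baseline; four demographic covariates unrelated to diabetes.
- 200,000 trials per cell. Monte Carlo SE is 0.05 point at 5%, 0.1 point at 80%, and about 0.2% on SD ratios.

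| R² | Model SE ÷ true SD, omitted | True SD, omitted ÷ included | CI width, omitted ÷ included | Type I error, omitted / included | Power at 0.81, omitted / included |
|---|---|---|---|---|---|
| 0 | 1.002 | 0.997 | 0.997 | 4.96% / 4.95% | 75.4% / 75.1% |
| 0.05 | 1.024 | 1.003 | 1.023 | 4.49% / 4.94% | 75.7% / 77.1% |
| 0.10 | 1.045 | 1.010 | 1.052 | 4.09% / 4.90% | 76.0% / 79.2% |
| 0.20 | 1.087 | 1.025 | 1.117 | 3.35% / 5.03% | 76.9% / 83.7% |

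The second column shows the standard error misstating its own sampling SD. The third shows the real precision lost, because incomplete blocks and dropout leave some imbalance. Together they account for the CI ratio, which matches step 2. The mean error of the estimate stays within 0.0015 of zero.

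**4. Sensitivity.**
- One demographic covariate correlated 0.4 with diabetes (R² = 0.05, 0.10, 0.20): CI ratio 1.018, 1.041, 1.097; type I error when omitted 4.71%, 4.32%, 3.75%; power lost 1.1, 2.8, 5.8 points. At R² = 0, including diabetes costs 0.4 point.
- 30% diabetic (40,000 trials): CI ratio 1.023, 1.051, 1.117.
- A separate simulation with baseline as the only other covariate and 30% or 50% diabetic (8,000 trials per cell): type I error when omitted 4.3–4.9%, 4.1–4.6%, 3.1–3.4%; power rises from 79–80% to 81%, from 80% to 83–84%, and from 81% to 87% when diabetes is included.

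**The case against.** The strongest reply is that omission is inferred. The demographic covariates are never listed, so the authors may have meant to include diabetes. The screening list in Protocol 4.0 does put "past medical and medicinal history" as an item separate from age, sex, race and ethnicity, but it is a flat data-collection list with no demographic heading, so it adds little. This stands as a limit on certainty. It does not supply the missing term: an analyst following the text as written would leave diabetes out, and no other section puts it in.

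Second, the size depends wholly on assumed values. Diabetes must predict 24-week change beyond baseline liver fat. The trial excludes "poorly controlled diabetes with A1C >9 within in the last six months" and requires stable anti-diabetic treatment, both of which may narrow the contrast. At R² = 0.02 the CI would be only about 0.7% wider and power about 0.4 point lower. This also stands, and the 20% case should be read as an upper illustration.

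Third, the promised power is not what is lost. With diabetes omitted, power rises slightly as diabetes becomes more prognostic. The gap between about 75% and 80% in the table is already there at R² = 0 and comes from the four non-prognostic covariates assumed there. That is correct: the loss is relative to the better model. Together with the conservative direction of the error, it makes this an efficiency point and not a threat to validity.

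**Conclusion.** The concern holds. The only factor used to stratify randomisation is not named in the primary or secondary model, and on a plain reading it is not covered by the demographic covariates. For any endpoint on which diabetes is prognostic, the CI is wider than the design warrants and the test runs below its nominal level. Over the assumed R² range of 0.05 to 0.20 the CI is about 2% to 12% wider and power at 0.81 is about 1 to 7 points lower than with the stratum included. At 0.05 or below the effect is small, and at zero nothing material is lost. Confidence is medium, because the documents give neither the prevalence of diabetes nor its prognostic strength. The change is worth making because the trade is one-sided: at most about 0.4 point of power is risked.

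**What to change.** In the SAP and in Protocol 8.0, state that the primary ANCOVA and each secondary ANCOVA include the diabetes stratum, as randomised, as a fixed covariate alongside treatment, the baseline value of the response and the covariates already planned. Naming the demographic covariates in the same sentence would remove the remaining doubt about what the model contains.

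The cost of adding the stratum is one phrase in each document and one degree of freedom. Diabetes status must already be known to randomise, so no new data are needed. The sample size does not change.
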